## SCHEDULE OF ACTIVITIES

	Pre-Procedure	Procedure	Post-Procedure	90-day BY PHONE	180-day	Un-Scheduled Visit
		Day (0)	(24-hours post-procedure or hospital discharge)	±14-days	±30-days	
Patient Eligibility Criteria	X					
Submit to Eligibility Committee						

 
• Clinical history
 
• Unruptured Intracranial Aneurysm Treatment Score
 
• Treatment plan
 
• ≥ 4 angiographic (DSA or CTA/MRA) images
 
	X					
Medical History	X 					
Digital Subtraction Angiography (DSA), Computed Tomography Angiography (CTA), or Magnetic Resonance Angiography (MRA)/Magnetic Resonance Imaging (MRI) of the brain/head	X 				X 	
Clinical assessment & Physical exam including:						

 
• Modified Rankin Scale (mRS)
 
• National Institutes of Health Stroke Scale (NIHSS) scale
 
	X		X	X 	X 	X 
Raymond Grade-Roy Occlusion Classification Scale	X 	X			X	
Laboratory Tests: hemoglobin, hematocrit, activated partial thromboplastin time, platelet count, international normalized ratio, pregnancy test, serum creatinine and glomerular filtration rate.	X 		X 			
Procedure Parameters		X				
Catheter Angiography		X 				
Contrast volume		X				
Record of AEs		X	X	X	X	X
Data for aneurysm assessment e.g. tortuosity, proximal & distal vessel diameter, target aneurysm measurements.		X			X	

 Within 7 days of index procedure.

 If performed under standard hospital procedure.

 For previously coiled aneurysms.

 Female subjects of child-bearing potential must have negative pregnancy test (urine or serum).

 Includes angiograms in the anterior posterior, lateral and working positions for analysis by a core laboratory.

 Telephone assessment and mRS is required. Other post procedure clinical assessment (scales/scores/grades) is left to the discretion of the investigator and shall be dictated by the patient's clinical symptoms.

 Post scans will be sent to the core laboratory for analysis.

 mRS is required. Other post procedure clinical assessment (scales/scores/grades) is left to the discretion of the investigator and shall be dictated by the patient's clinical symptoms.

 If visit is related to target aneurysm or potentially associated AE/SAE

## 1. INTRODUCTION

### 1.1 Device Name

CorPath® GRX System

### 1.2 Background

Subarachnoid hemorrhage is a life-threatening form of stroke with an estimated fatality rate between 26 and 36%. In approximately 80% of cases, subarachnoid hemorrhage is caused by the rupture of an intracranial saccular aneurysm. Aneurysms occur when structural abnormalities in the walls of the cerebral arteries cause weakening, thinning, and out-pouching of the vessel wall. They are frequently located at bifurcations within the proximal circle of Willis and approximately 20-50% of such aneurysms eventually rupture. While the incidence of subarachnoid hemorrhage varies widely from country to country and may be as high as 15 to 20 per 100,000 in Finland and Japan, its overall worldwide incidence is estimated to be 9.1 per 100,000 persons. As many as 30,000 Americans are affected per year.

Patients who survive subarachnoid hemorrhage long enough to be stabilized medically may experience cerebral vasospasm, delayed cerebral ischemia, hydrocephalus, deep venous thrombosis, and numerous medical sequelae, along with long-lasting neuropsychological changes, loss of productive years, and diminished quality of life. They are also at serious risk of re-rupture, and therefore it is usually appropriate for them to undergo treatment to minimize aneurysmal recurrence or re-rupture.

Meanwhile, it has been estimated that the remaining 50% to 80% of intracranial aneurysms present in the general population never rupture. The prevalence of unruptured intracranial aneurysms (UIA) in the general adult population has been estimated at between 1% and 5%, based on autopsy studies. Many are asymptomatic and detected only as incidental findings during cerebral imaging for other conditions. Others may cause headaches, seizures, cranial nerve palsies, focal neurologic deficits, and distal embolic ischemic events.

Due to the severe consequences of aneurysmal rupture, once a UIA is detected, a decision must be made between managing the patient conservatively or treating the aneurysm to prevent future rupture. While current clinical evidence favors treatment for ruptured aneurysms, the

decision to intervene for UIA is less straightforward and must balance the risk-benefit profile of the available interventions against the risks and benefits of watchful waiting.

Whether to prevent primary rupture of a UIA or re-rupture following a subarachnoid hemorrhage event, the principal treatment options are open surgical clipping or endovascular coiling. Surgical clipping involves a craniotomy, through which the aneurysmal sac is closed mechanically by placing a titanium clip over the neck. Endovascular coiling is achieved percutaneously by threading a catheter from the femoral artery, accessed at a site in the groin, up through the arterial circulation to the neck of the aneurysm. Using the catheter as a guide, a smaller microcatheter is then advanced through the guide catheter to the target aneurysm. After placement of the microcatheter, a metal wire is inserted into the microcatheter and advanced up to and into the aneurysmal sac, where the wire is gently pushed forward, causing it to coil around itself until it fills the volume of the sac. The presence of the metal coil induces thrombosis, occluding the aneurysm and preventing turbulent or high-pressure blood flow that is the precursor to thrombogenesis or rupture.

Available evidence is not sufficient to definitively favor one technique over the other, but some randomized clinical trials have suggested that surgical clipping is effective and durable, while minimally invasive endovascular approaches result in better functional outcomes after 1 year. Presumably this difference is a result of the higher overall risks of open surgery compared to minimally invasive procedures. Nonetheless, the pace of adoption of percutaneous aneurysm coiling and other neuro-endovascular techniques continues to accelerate, and therefore there is advantage to the continuous development of technical measures that can improve their safety.

The risks of endovascular approaches generally fall into categories similar to those observed in percutaneous coronary and peripheral vascular intervention (PCI and PVI) and include intraprocedural rupture, arterial dissection, pseudoaneurysm, thromboembolism, occlusion of parent arteries, and groin hematomas and infections. Patients can also experience adverse reactions to the contrast material necessary for visualization of the procedure under fluoroscopy.

As a radiation-dependent imaging technique, fluoroscopic navigation further poses occupational risks to the clinical staff performing the procedure. Data from studies on healthcare professionals working in cardiac catheterization labs have suggested that long-term exposure to low-dose ionizing radiation is linked to elevated risk of cataracts, skin lesions, thyroid disease, premature vascular aging, and cancer compared to healthcare professionals not routinely exposed to occupational fluoroscopy. Furthermore, the protective clothing worn to shield interventionalists from fluoroscopy is bulky, heavy, and puts the clinical staff at non-trivial risk of ergonomic strain and orthopedic injury.

The advent of the CorPath GRX Robotic System for PCI and later for PVI has begun to address some of the limitations of endovascular intervention.

The CorPath GRX system translates the manual movements of the interventionalist into precision micromovements during navigation and facilitates precision measurement of anatomy to determine lesion length. It also allows the procedure to be performed from a remote, radiation-shielded workstation, which may help to reduce the interventionalist's exposure to ionizing radiation and orthopedic strain.

The field of neurosurgery also stands to benefit from the use of robotic assistance. To date, the ROSA robot (Zimmer Biomet, Warsaw IN, USA) has been FDA cleared and CE marked for epilepsy evaluation and spine surgery, the Modus V robotically operated exoscope (Synaptive Medical, Toronto, ON, Canada) is FDA cleared for subcortical surgery, and the Renaissance Surgical Guidance Robot (Mazor Robotics, Caesarea, Israel) is FDA cleared and CE marked for spine surgery.

However, until recently, no robotic platform has been designed to accommodate the micro guidewires, microcatheters, and micro-scale movements specific to successful neurovascular intervention.

Based the findings of an initial evaluation of the system in *in vitro* and animal neurovascular models, Corindus has recently implemented software and engineering modifications to its CorPath GRX Robotic System to address neuro-endovascular-specific needs and indications.

These modifications include:

*Version Date: May 21, 2021*

*This confidential document is the property of Corindus, Inc. and shall not be reproduced, distributed, disclosed or used without the express written consent of Corindus, Inc.*

- 1) A software feature called “Active Device Fixation (ADF)”. When enabled, ADF maintains the placement of both the guidewire and device while the catheter is advanced or retracted by advancing or retracting the guidewire and device to off-set the motion of the catheter.
- 2) A software feature called “Limited Speed”. When enabled, Limited Speed reduces the linear movement of the guidewire or device by half, capping its maximum speed at a rate of 6 mm/sec.
- 3) Physical modifications to the hardware to securely and reliably accommodate the smaller gauge devices common to percutaneous neurosurgery.
- 4) Software modifications to allow for increased working length to enable target access for microcatheters and an updated user interface to accommodate the new workflow and automated movements. These new features have been further evaluated in vitro and in vivo, with results that suggested that clinical development of the modified system is war- ranted (Britz et. al., 2019, Manuscript in Preparation).

The present clinical study is a prospective, single-arm, international, multi-center, non-inferiority study to evaluate the effectiveness and safety of the CorPath GRX System for endovascular cerebral aneurysm embolization compared to historical controls through 24-hours post-procedure or hospital discharge, whichever occurs first.

## **2. INTENDED USE & DEVICE DESCRIPTION**

### **2.1 Intended Use**

The CorPath GRX System is intended for use in the remote delivery and manipulation of interventional devices during percutaneous coronary and vascular procedures, including the following commercial devices:

- Guidewires
- Rapid Exchange Catheters
- Guide Catheters
- Microcatheters
- Embolization Coils

- Coil Assist Stents

## 2.2 Device Description and Mode of Operation

The CorPath GRX System is designed to allow the operator to remotely manipulate interventional devices within a patient's vasculature to perform vascular procedures in a precise and well-controlled fashion, without being exposed to radiation levels typically encountered during a conventional (i.e. manual) procedure. The complete CorPath GRX System includes the following major components:

### 2.2.1 Bedside Unit

The Bedside Unit consists of an Extended Reach Arm, Robotic Drive, and Single-use Cassette.

- Extended Reach Arm: Mounted on the rail of the procedure table and supports the Robotic Drive.
- Robotic Drive: Receives inputs from the Control Console. These inputs actuate mechanical operations in the Single-use Cassette as movements to a loaded guidewire, device, and guide catheter/microcatheter. The Robotic Drive moves forward and backward to advance and retract the guide catheter or microcatheter. A Bedside Touchscreen on the Robotic Drive provides the user interface for the bedside operator during system set-up, loading, and device exchanges.
- Single-use Sterile Cassette: Attaches to the Robotic Drive and can be loaded with commercially available guidewires, rapid exchange catheters, guide catheters, microcatheters, neuro- vascular stent retrievers, embolization coils, and intracranial stents. This Single-use Cassette advances and retracts the guidewire, device and catheter, with the ability to rotate the guidewire and catheter.

**Note:** Refer to specific interventional device instructions for proper device use.

### 2.2.2 Interventional Cockpit

The interventional cockpit houses the Control Console, X-ray Foot Pedal, and Monitor(s) to display angiographic and hemodynamic data. It is designed to protect the physician from radiation exposure while maneuvering interventional devices.

### 2.2.3 Control Console

This component has a touchscreen and three joysticks (one joystick for device manipulation, one joystick for guidewire manipulation and one joystick for catheter manipulation). The device joystick allows for precise control of linear motion (advancement and retrieval) of its respective devices. The guidewire joystick allows for both linear and rotational movement (clockwise and counterclockwise) of the guidewire. The catheter joystick allows for precise control of linear motion (advancement and retrieval) and for rotational movement (clockwise and counterclockwise) of the guide catheter or microcatheter. The devices are controlled independently, which allows operations to be performed individually (by using one joystick at a time) or simultaneously (by activating multiple joysticks at once). For precise, discrete manipulation, the device, guidewire and catheter can also be manipulated in discreet 1-mm increments via the touch-screen buttons on the Control Console.

CorPath GRX features technIQ Smart Procedural Automation, a set of automated movements unique to the system. These movements include: Rotate on Retract (RoR), Limited Speed, and Active Device Fixation (ADF). Users may enable a technIQ by pressing on the dropdown menu on the corresponding section of the touchscreen on the Control Console.

**Note:** For a more detailed description of the CorPath GRX System please refer to the CorPath GRX System Operator's Manual.

### 2.2.4 Device Accountability

According to the ISO 14155:2020, Section I.7, part C, point 1, if a device is a market approved medical device being used within its approved indication, device accountability is not required. In addition, point 2 states that labelling specific for clinical investigations is also not required.

### 3. OBJECTIVES & ENDPOINTS

#### 3.1 Study Objective

The primary objective of this study is to evaluate the effectiveness and safety of robotic-assisted endovascular embolization procedures compared to objective performance criteria based on the scientific literature.

#### 3.2 Primary Effectiveness Endpoint

The primary effectiveness endpoint will be defined as successful completion of the robotic-assisted endovascular procedure absent any unplanned conversion to manual for guidewire or microcatheter navigation, embolization coil(s) or intracranial stent(s) deployment, or an inability to navigate vessel anatomy.

#### 3.3 Primary Safety Endpoint

The primary safety endpoint will be a composite of intra- and peri-procedural events, defined as vascular injury including intraprocedural aneurysm rupture caused by robotically controlled catheters, wires, or devices and thromboembolic events with neurological decline (NIHSS score change  $\geq 4$ ) within 24-hours post-procedure or hospital discharge, whichever occurs first.

#### 3.4 Secondary Endpoints

Several secondary endpoints will be examined in this trial, including the following:

- 1. Clinical Outcome** - Clinical outcome as measured by Modified Rankin Scale. This is assessed at 90-Day Follow-Up ( $\pm 14$  days) and 180-Day Follow-Up ( $\pm 30$  days from the procedure date);
- 2. Robotically Navigate Device to the Target Aneurysm** - Defined as successful advancement of devices to the target aneurysm robotically;
- 3. Robotically Navigate Device *into* the Target Aneurysm** - Defined as successful navigation of device into the target aneurysm robotically;
- 4. Robotically Deploy Therapeutic Device *into* Target Aneurysm** - Defined as successful deployment of therapeutic device into the target aneurysm robotically;
- 5. Overall Procedure Time** - Defined as the time measured from the insertion of the access sheath/catheter until the removal of the microcatheter;

6. **Robotic Procedure Time** - Defined as the time measured from the first device used robotically until the removal of the microcatheter;
7. **Fluoroscopy Time** - Total fluoroscopy utilized during the procedure as recorded by the Imaging System;
8. **Patient Radiation Exposure** - DAP (dose-area-product) and CD/AK (cumulative dose/air kerma) as recorded during the procedure;
9. **Contrast Volume** - Total contrast used during the procedure;
10. **Adverse Events** - All adverse events (AEs) from the start of the CorPath GRX procedure until the end of the study will be summarized.
11. **Thromboembolic Events** - Defined as rate of thromboembolic events occurring up to 180-days following the robotic-assisted procedure;
12. **Devices Used Robotically** - All devices used will be recorded as successful or unsuccessful in conjunction with the CorPath GRX System;
13. **Aneurysm Occlusion** - Angiographic assessment of aneurysm occlusion grade according to the Raymond-Roy classification scale, parent-vessel compromise, and occlusion durability as assessed from an independent core laboratory. This will be assessed post-procedure and at a 180-day follow-up.

## 4. INVESTIGATIONAL PLAN

### 4.1 Overview of Trial Design

This is a prospective, single-arm, international, multi-center, non-inferiority study to gather real-world data on the effectiveness and safety of the CorPath GRX System for endovascular cerebral aneurysm embolization. Subject selection requires a clinical indication for endovascular coil and/or stent-assisted coiling embolization of cerebral aneurysms. After obtaining informed consent, performing eligibility confirmation, then screening and baseline assessments, qualifying subjects will be enrolled in the clinical investigation.

The study will be conducted at a maximum of up to 20 investigational sites. This will depend on each active site's recruitment rate and the possible travel restrictions due to the Covid-19 pandemic. Up to 120 subjects will be enrolled in order to achieve at least 108 subjects in the study; each site will try to recruit a maximum of 20 subjects. If a site has the possibility to enroll

Version Date: May 21, 2021

*This confidential document is the property of Corindus, Inc. and shall not be reproduced, distributed, disclosed or used without the express written consent of Corindus, Inc.*

more than 20 subjects, a written authorization will be required from the sponsor, Corindus, Inc. The protocol does not dictate the therapeutic decisions of the Investigators. The total expected maximum *clinical investigation duration*, including completion of all follow-up requirements, is approximately 24 months: the recruitment phase is 18 months and follow-up is 180-days. No further follow-up or additional treatment is required per the protocol, and any additional follow-up and/or treatment is at the discretion of the physician/standard hospital practices.

All enrolled subjects will be followed post-CorPath GRX endovascular procedure through 180 days post-procedure.

#### **4.2 Roll-in Subjects**

The primary purpose of the roll-in subjects is to allow the Investigator to gain experience with the CorPath GRX System in the setting of the clinical trial. This will also ensure familiarity with protocol requirements. The first three (3) subjects for each primary Investigator will be considered as roll-in subjects. Subjects entered in the roll-in phase will complete all follow-up requirements of 180-days.

#### **4.3 Enrollment Plans**

Each consecutive patient undergoing a CorPath GRX cerebral aneurysm endovascular procedure will be enrolled in the study after providing written informed consent for the provision of data.

#### **4.4 Informed Consent Procedures**

This protocol requires written informed consent, in accordance with applicable country and clinical investigation site regulations. This consent shall be obtained from each conscious subject prior to the investigational procedure. The subject will have at least 24 hours to consider if he/she wants to participate in the study (if required by EC).

Although not indicated in the Patient Information Sheet, in certain countries, the Ethics Committee requires that all subjects included in the clinical investigation be affiliated with their respective national social security system. It is up to the investigator to find out if the subject has this required affiliation.

Prior to starting the clinical investigation, Corindus will provide the Principal Investigator with a

*Version Date: May 21, 2021*

*This confidential document is the property of Corindus, Inc. and shall not be reproduced, distributed, disclosed or used without the express written consent of Corindus, Inc.*

copy of the Informed Consent Document approved by the Ethics Committee (EC) and the Competent Authority (if applicable), with documented evidence that the protocol has received EC and Competent Authority (if applicable) approvals.

A thorough written explanation will be provided to the subject as to the nature and objectives of this study. Details of the study should include (but are not limited to) the following terms:

- Purpose of the study
- Alternative treatments
- Participation is voluntary, and there is no penalty for withdrawal
- Potential risks/benefits for participation
- Contact information to ask questions or voice concerns

This discussion should highlight the fact that the patient is being asked solely to share the data collected from their endovascular robotic procedure and any related events through 24-hours post-procedure or discharge, whichever occurs first. The study investigator and/or staff are responsible for obtaining written informed consent from each potential subject before any study specific procedures required by the protocol are performed. Informed consent should be obtained in written format and using a form approved by the EC and Competent Authority. The form should contain standard language consistent with local policies for ensuring privacy of confidential information. All subjects must sign the informed consent prior to any procedures/tests that go beyond initial assessments associated with the standard care for subjects with cerebral aneurysms and before any study related treatment assessments are administered and subject-related health information can be entered into the study database.

Subjects are considered enrolled in the study once the subject signs the study Informed Consent Form. Failure to obtain signed informed consent, renders the subject ineligible. For those subjects that sign informed consent, a copy shall be kept in the subject's medical records and study files. A copy of the fully executed informed consent form must be given to each subject enrolled in the study.

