## STUDY DURATION/ FOLLOW-UP PERIOD

The recruitment phase is 18 months, follow-up is 180-days, and total study duration is 24 months. All subjects will be followed post-CorPath GRX endovascular embolization procedure through 180-days.

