#### 4.8.10 Follow-Up Evaluations

The following assessments will be completed at the specified time points below.

- 90-Day Follow-Up ( $\pm$  14 days) via a telephone evaluation**
  - Functional outcomes assessment to include Modified Rankin Scale (mRS)
  - Record any adverse events or additional interventions since time of hospital discharge
- 180-Day Follow-Up ( $\pm$  30 days)**
  - Digital Subtraction Angiography (DSA), Computed Tomography Angiography (CTA), or Magnetic Resonance Angiography (MRA) / Magnetic Resonance Imaging (MRI) of the brain/head
  - Functional outcomes assessment to include Modified Rankin Scale (mRS)
  - Raymond-Roy Occlusion Classification
  - Record any adverse events or additional interventions since time of hospital discharge.

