The Corindus CorPath GRX Neuro trial is a prospective, single-arm, international, multi-center, non-inferiority study to evaluate the effectiveness and safety of the CorPath GRX System for endovascular cerebral aneurysm embolization compared to historical controls. Subject selection requires a clinical indication for endovascular coil and/or stent-assist coiling embolization of cerebral aneurysms.

The CorPath GRX System is intended for use in the remote delivery and manipulation of interventional devices during percutaneous coronary and vascular procedures. The CorPath GRX System is designed to allow the operator to remotely manipulate interventional devices within a patient's vasculature to perform vascular procedures in a precise and well-controlled fashion, without being exposed to radiation levels typically encountered during a conventional (i.e., manual) procedure. The complete CorPath GRX System includes a bedside unit, interventional cockpit, and control console.

The recruitment phase is 18 months, follow-up is 180 days, and total study duration is 24 months. All subjects will be followed post-CorPath GRX endovascular embolization procedure through 180 days.

The subject population is subjects with a clinical indication for endovascular coil and/or stent-assisted coiling embolization of cerebral aneurysms. Up to 120 subjects will be enrolled in order to achieve at least 108 subjects in the study; each site will try to recruit a maximum of 20 subjects.

The data collection schedule is provided in Table 1 below.

Table 1. Data collection schedule

	Pre-procedure	Procedure	Post Procedure
			(24 hours post-procedure or hospital discharge)
Patient Eligibility Criteria	X		
Medical History	X ¹		
Head CT angiography or MRI angiography	X ¹		
Clinical assessment & Physical exam: including: 
• Hunt and Hess scale• Modified Rankin score• Raymond Grade for previously coiled aneurysms• National Institutes of Health Stroke Scale (NIHSS) scale• World Federation of Neurological Surgeons (WFNS) Subarachnoid Hemorrhage (SAH) Grade• Fisher grade	X ¹		X
Raymond Grade-Roy Occlusion Classification Scale	X ³		X
Laboratory Tests: complete blood count, hemoglobin, platelet count, platelet function testing, pregnancy test, serum creatinine and glomerular filtration rate.	X ^{1,2,4}		X ²
Procedure Parameters (CorPath GRX use, procedure time, fluoroscopy time, patient radiation exposure, etc.)		X	
Angiography		X ⁵	
Contrast volume		X	

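### Protocol 4.4 has sites describe data sharing as ending at 24 hours or discharge, although every subject is followed to 180 days

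*Protocol*

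**What the plan says.** Protocol 4.4 (Informed Consent Procedures) tells staff what to stress when they discuss the study with a patient: "the patient is being asked solely to share the data collected from their endovascular robotic procedure and any related events through 24-hours" after the procedure, with discharge as the cut-off if it comes earlier. This is current Revision I text.

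Elsewhere the plan runs to 180 days for everyone:

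- Protocol summary: "The recruitment phase is 18 months, follow-up is 180-days, and total study duration is 24 months".
- Protocol 4.1: "All enrolled subjects will be followed post-CorPath GRX endovascular procedure through 180 days post-procedure".
- Protocol 4.2: "Subjects entered in the roll-in phase will complete all follow-up requirements of 180-days".
- SAP, introductory description: "All subjects will be followed post-CorPath GRX endovascular embolization procedure through 180 days".
- Protocol 4.8.10 and Table 1: an mRS by telephone at 90 days; at 180 days, brain imaging, mRS and Raymond-Roy grade; adverse events at both contacts. A Table 1 footnote sends the follow-up scans to the core laboratory.
- Protocol 5.5: adverse events are reported from consent until the subject leaves the study.

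**The concern.** The word solely makes the sentence in 4.4 exclusive. A site that follows it tells the patient that nothing after 24 hours or discharge will be shared, and then telephones at 90 days, asks for imaging at 180 days and sends the scans to a core laboratory. The instruction applies to every subject, up to 120 of them.

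Consent also carries weight in this protocol. Section 4.3 ties enrolment to consent for supplying data, and 4.4 makes the signature a precondition for entering health information in the study database. If the described scope is too narrow, a subject might decline follow-up that was not mentioned, or the use of late data might be questioned. For the late endpoints, Protocol 6.9 and SAP section 5 rely on follow-up effort and give no analytic method for missing values. A discussion that omits the follow-up works against that effort.

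**Working it through.** No power or margin calculation applies. The check has four steps.

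**1. Is the 180-day follow-up built into the plan?** Inputs from the protocol summary: 18 months of recruitment, 180 days of follow-up, 24 months in total. With 365.25 / 12 = 30.44 days per month, 180 / 30.44 = 5.9 months, and 18 + 5.9 = 23.9 months, which reproduces the stated 24. With the +30-day visit window, 210 / 30.44 = 6.9, giving 24.9 months. If data collection stopped at 24 hours or discharge, the total would be about 18 months. The stated duration therefore depends on the 180-day follow-up.

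**2. The texts side by side.**

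| Item | Consent discussion (4.4) | Rest of the plan |
|---|---|---|
| End of data sharing | 24 hours or discharge | 180-day visit (summary, 4.1, 4.2, 4.8.10, SAP) |
| Events covered | "any related events through 24-hours post-procedure or discharge, whichever occurs first" | All adverse events, related to the device or not (5.1), to study exit (5.5) |
| Telephone contact | Not mentioned | 90 days, mRS |
| Later imaging | Not mentioned | 180 days, with core laboratory review |

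Nothing else in 4.4 extends the window. Section 11.1 says the consent form must describe the study adequately, but gives no time frame.

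**3. Which endpoints need data from outside the window?** From the 13 secondary endpoints in Protocol 3.4:

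- Wholly outside: mRS at 90 and 180 days (no. 1).
- Partly outside: adverse events to end of study (no. 10), thromboembolic events to 180 days (no. 11), aneurysm occlusion after the procedure and at 180 days (no. 13).
- Inside: the other 13 − 4 = 9, all procedural.

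**4. Primary endpoints and sample size.** Effectiveness (3.2) is settled during the procedure. Safety (3.3) closes at 24 hours or discharge. Both lie inside the described window. The sample sizes in 6.6 (96 for safety, 108 for performance) rest on these two endpoints alone.

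**Likely origin, as inference only.** The revision history lists the 90- and 180-day follow-up among the Revision I changes for all sites and does not list 4.4 among the sections changed. Two other places keep the short horizon: the last paragraph of section 1.2, and the SAP's data collection table, which has no 90- or 180-day column although the SAP text states 180 days. This fits a sentence left behind when follow-up was extended, but the contradiction stands in the current text whatever its origin.

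**The case against.** The best defence is that one sentence in 4.4 is not the consent process. Section 4.4 also calls for a full written account of the study and a form approved by the Ethics Committee and Competent Authority. Section 11.1 has that form submitted together with the protocol and requires it to inform subjects adequately. The form may well describe the 180-day follow-up. Section 4.8.9 further recommends confirming contact details before discharge so that the 90-day call can be scheduled, which makes a surprise call less likely. The sentence can also be read as contrasting the supply of data with receiving an experimental treatment, since section 11.1 describes a post-market study. Finally, the verb is should, so the text advises and does not strictly require.

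Much of this stands, and it limits the consequences. A reader might infer that the late data fall outside consent and cannot be used, or that all subjects need re-consent. The documents support neither: they do not contain the consent form, and no passage shows that any subject signed one limited to 24 hours. The defence does not remove the contradiction, however. On the post-market reading the 24-hour limit is still wrong, and if the form is right, 4.4 tells staff to stress something that the form contradicts.

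**Conclusion.** The contradiction is real and sits in an operative instruction. It concerns what sites are told to say to every subject, and it bears on four of 13 secondary endpoints, one wholly and three in part. Protocol 6.3 treats secondary endpoints descriptively.

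It does not touch either primary endpoint, the performance goals or the sample size, so it should not be read as weakening the trial's main conclusions. Harm to the late data is possible but unverified, because it depends on the wording of the approved forms and on local rules, neither of which is in the documents. The correction is worth making because the instruction is wrong as written and cheap to repair.

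**What to change.** 1. Reword the sentence in Protocol 4.4 so that the data described run through the 180-day visit. Name the 90-day call, the 180-day imaging with core laboratory review, and adverse events to study exit.
2. Align the last paragraph of section 1.2, either by adding the 180-day follow-up or by saying that the 24-hour horizon applies to the primary comparison.
3. Confirm that each consent form version in use covers this follow-up. Only if a version is found limited to 24 hours, refer re-consent of the subjects who signed it to the Ethics Committee before their late data are used.

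The cost is two wording changes in a protocol amendment and a check of consent versions. Re-consent would add work only if that check fails. No endpoint, margin or sample size changes.
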